
EXCLUSION CRITERIA
	
 
1. Subjects in whom flexible bronchoscopy is contraindicated
 
2. Target nodule < 1.0 cm
 
3. Prior radiation or neo adjuvant chemotherapy of the target nodule/tumor
 
4. Any comorbidity that the investigator feels would interfere with the safety of the subject or the evaluation of study objectives
 
5. Pacemaker, implantable cardioverter, or other electronic implantable device
 
6. Patients with coagulopathy
 
7. Patients in other therapeutic lung cancer studies
 
8. Subject is pregnant or breastfeeding
 
9. Known or suspected sensitivity or allergy to nickel
 

TREATMENT ALGORITHM
	
The target nodule/tumor depth will be measured under EBUS visualization. The applied energy will be determined based on the nodule/tumor size using guidance from the Instructions for Use (IFU) to create a measurable and predictable ablation zones. A single ablation zone will be created in the first 3 subjects. The applied energy and number of ablation zones for the remaining subjects will be determined based on the nodule/tumor size and physician defined target ablation zone(s).

PATHOLOGY ASSESMENT
	
The ablated target nodule/tumor and surrounding tissue will be resected. The specimens will be examined by gross, histopathologic, and may be assessed by immuno-histochemical methods. Routine staining will be performed with hematoxylin and eosin (H&E). Analysis of cellular vitality may be performed with different methods of immunostaining which may include one or more of the following: including mouse antihuman mitochondria monoclonal antibody (MAB 1273), TUNEL, Ki167 PHH3, and Masson's trichrome.
 
The pathology assessment will be performed by an experienced pathologist.

IMMUNE RESPONSE
	
Blood will be drawn pre and post ablation to assess for immune response indicators
 
The micro environment of the resected tissue may have pathological assessment for immune cell population to explore a potential mechanistic effect of immune response.

FOLLOW-UP
	
Subjects will be followed peri-operatively for safety. There is no long-term follow-up since the ablated tissue will be resected during the scheduled post-ablation surgical procedure, however adverse events will be captured 30 days post-procedure.

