#### 4.1.2 Secondary Endpoints

- 1) Pathological and immuno-histochemical evaluation of the acute thermal effect, produced by the ANET device, on targeted pulmonary nodule/tumor and surrounding tissue to determine if the observed zone of ablation is localized and consistent with the predicted zone of ablation.
- 2) Characterize any effects on surrounding tissue outside the zone of predicted ablation.

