### 7.2.6 Pathology

The tumors will be bisected through the largest diameter in a right angle referring to the RFA electrode direction and marked to determine orientation of coagulation electrode immediately after the resection procedure. The specimens will be fixed in 10% neutral buffered formalin-solution and prepared for routine diagnostics and immuno-histochemistry.

The specimens will be examined by gross pathology, histopathology, and may be examined by immuno-histochemical methods. Routine staining will be performed with hematoxylin and eosin (H&E). Analysis of cellular vitality may be performed with different methods of staining, which may include one or more of the following: mouse antihuman mitochondria monoclonal antibody (MAB 1273; Millipore UK, Hertfordshire, UK), Terminal deoxynucleotidyl transferase-mediated nick end-labeling (TUNEL; Boehringer Ingelheim, Germany), antibody MiB1(Ki67; Dianova, Hamburg Germany), PHH3, and Masson's trichrome The immuno-histochemical criterion for cell death in is the lack of expression or proliferation/mitotic index markers in the treated and surrounding tissue. The intent of the pathology assessments is to determine if the observed zone of ablation is consistent with the predicted zone of ablation and to characterize any effects on surrounding tissue outside the zone of predicted ablation.

---

 Schneider et al., "Intraoperative Radiofrequency Ablation of Lung Metastases and Histologic Evaluation."

 Thomas Schneider et al., "The Efficacy of Bipolar and Multipolar Radiofrequency Ablation of Lung Neoplasms - Results of an Ablate and Resect Study," *European Journal of Cardio-Thoracic Surgery: Official Journal of the European Association for Cardio-Thoracic Surgery* 39, no. 6 (June 2011): 968–73, doi:10.1016/j.ejcts.2010.08.055.

 Clasen et al., "Pathomorphologic Evaluation of Pulmonary Radiofrequency Ablation."

 Ibid.

 Pelosi et al. *J Thorac Oncol.* 2014;9: 273–284

 Ozturk Sari et al. *Endocr Pathol.* 2016 Jun;27(2):162-70

 Jie Ouyang et al. Utility of desmin and a Masson's trichrome method to detect early acute myocardial infarction in autopsy tissues, *Int J Clin Exp Pathol* 2010;3(1):98-105.

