 T.D. Koreckij et al., Low Dose, Alternating Electric Current Inhibits Growth of Prostatic Cancer, *The Prostate*, Accepted 5 October 2009, Published online in Wiley InterScience (www.interscience.wiley.com).

The micro environment of the resected tissue may have pathological assessment for immune cell population to explore a potential mechanistic effect of immune response..

The pathologic and immuno-histochemical effect of RFA on nodules/tumors and surrounding tissue will be evaluated by an experienced pathologist.

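### Section 7.2.6 sets no masking and no reading order for the observed-zone measurement, so secondary endpoint 1 is open to expectation bias

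*Combined protocol and SAP*

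**What the plan says.** Section 4.1.2 defines secondary endpoint 1 as a pathological evaluation of the acute thermal effect "to determine if the observed zone of ablation is localized and consistent with the predicted zone of ablation". Secondary endpoint 2 covers effects beyond the predicted zone.

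Section 7.2.6 carries both into the pathology work. It says "The intent of the pathology assessments is to determine if the observed zone of ablation is consistent with the predicted zone of ablation", and it adds a second aim, "to characterize any effects on surrounding tissue outside the zone of predicted ablation". On who does this, the synopsis says "The pathology assessment will be performed by an experienced pathologist", and 7.2.6 says that the effect on tumor and "surrounding tissue will be evaluated by an experienced pathologist".

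The prediction comes from the treatment side. According to the synopsis, energy follows nodule or tumor size under the IFU. After the first 3 subjects, the physician's own target zone or zones also enter. The only procedural information said to travel with the specimen is the electrode direction: the tumor is bisected and "marked to determine orientation of coagulation electrode immediately after the resection procedure".

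Section 12 plans summary results without a hypothesis and does not mention the pathology endpoints.

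**The concern.** The edge of an acute thermal zone is partly a matter of judgement. A reader who already knows where the edge is expected may place it nearer to that position than the tissue warrants. If the zone is outlined with the prediction in view, agreement between the two is partly built in.

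This matters because section 4.1 gives the study a performance objective as well as a safety one, and both performance endpoints rest on this pathology work. Anchoring on the prediction could conceal overshoot, which bears on safety, as well as undershoot, which bears on performance. It cannot be undone afterwards: once the prediction has been seen, an independent first measurement by that reader is no longer possible.

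**Working it through.** The plan gives no figure for zone agreement or for reader error, so there is none to reproduce. The main check is a comparison of the text.

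**1. Does the read need the prediction?** Yes, at some stage. Both aims in 7.2.6 refer to the predicted zone, and the second cannot be completed without its boundary.

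**2. Is the observed zone fixed before the prediction is used?** The synopsis and sections 4.1.2, 5.1, 5.2, 7.2.5, 7.2.6 and 12 give no masking, no reading order, no locked first measurement, no second reader and no adjudication. They do not name the dimension to be recorded or describe a form for the prediction. Section 5.2 names a core laboratory for blood only.

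**3. Is there room for judgement at the edge?** Four places suggest so.
- Section 5.2 puts resection directly after ablation. In the short-term swine study (section 3) tissue was taken at 7 days, which that study's pathologist regarded as the best time to see cell killing.
- The same swine study reports some variation between animals in the pattern of thermal effect. The long-term study describes full coagulation giving way to selective cell damage with distance, which is a graded margin.
- Section 7.2.6 commits only to H&E; the vitality stains there are optional. Sections 4.1.2, 5.1 and 5.2 read as if immuno-histochemistry will be done. Even then, the marker criterion for cell death comes with no rule for tracing or measuring the zone.
- Section 1 says that imaging does not adequately characterize lethal zones extending past a tumor, so CT is a weak cross-check.

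**4. Scale, under assumptions.** Suppose each of 10 subjects is called consistent or not, which the plan does not specify. Let p be the true proportion consistent and b the share of truly inconsistent zones that a reader aware of the prediction calls consistent. Both are assumed. The recorded proportion is q = p + (1 − p)b, the expected count is 10q, and P(at least 9 of 10) = 10q⁹(1 − q) + q¹⁰.

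| p | b | q | Expected count | P(at least 9 of 10) |
|---|---|---|---|---|
| 0.5 | 0 | 0.50 | 5.0 | 0.011 |
| 0.5 | 0.2 | 0.60 | 6.0 | 0.046 |
| 0.5 | 0.5 | 0.75 | 7.5 | 0.244 |
| 0.7 | 0 | 0.70 | 7.0 | 0.149 |
| 0.7 | 0.2 | 0.76 | 7.6 | 0.267 |
| 0.7 | 0.5 | 0.85 | 8.5 | 0.544 |
| 0.9 | 0 | 0.90 | 9.0 | 0.736 |
| 0.9 | 0.2 | 0.92 | 9.2 | 0.812 |
| 0.9 | 0.5 | 0.95 | 9.5 | 0.914 |

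Even without any reader error, 10 of 10 has an exact 95% interval of 69.2% to 100%, since 0.025^(1/10) = 0.692. The table shows how a summary count would respond to a given b. It is not evidence that b exceeds zero.

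**The case against.** The strongest reply is that the protocol is silent, and silence is not a defect in conduct. A reader might infer that the pathologist is unmasked, outlines the zone personally, and is instructed to rule on the match. The documents say none of these things. Section 7.2.6 states the intent of the assessments; it does not assign the outlining or the comparison to a person, and electrode orientation is all that is said to accompany the specimen. This stands, and it limits the point to what the plan leaves open.

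A reader might also infer that nothing else could reveal a misread zone. That goes too far. Post-ablation bronchoscopy and chest CT are required (7.2.3), device-related adverse events are the primary endpoint, and secondary endpoint 2 looks outside the predicted zone. These are partial checks: CT has the limit noted in section 1, and endpoint 2 comes from the same pathology work.

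Nor do the 3.1 cm cap and the 2 cm distance from critical structures in 7.2.2 give a size for the problem. They describe the physical zone, whoever reads the slide, and the target zone lies wholly within the planned resection (5.1).

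Finally, it can be said that reading order is secondary while consistency has no definition. The missing definition is a separate gap. A locked measurement is useful without one, because the difference from the prediction can be reported directly.

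**Conclusion.** The point holds as a risk. Following 7.2.6 as written leaves secondary endpoint 1 open to expectation bias, because the prediction is part of the task and nothing requires the observed zone to be fixed first. Drift toward agreement is the plausible direction, but the documents do not support saying that the endpoint is biased, and the size cannot be estimated from them.

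The consequence is limited. The endpoint is secondary and descriptive, there are up to 10 subjects, no hypothesis is tested, and the primary endpoint is defined by adverse events and not by this read. The conclusion rests on two assumptions: that placing the edge of an acute zone involves judgement, which the swine findings support, and that no unpublished pathology manual already sets a reading order. The change is worth making because it is cheap and has to be in place before the first specimen is read.

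**What to change.** Add a two-step read to 7.2.6.

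- **Before resection:** record the predicted zone dimensions for each ablation.
- **Step 1, masked:** the pathologist, given only the electrode orientation, measures, signs and locks the observed zone dimensions. The same form records all thermal effects seen in the specimen, with their location relative to the electrode. The predicted zone, the energy settings and the post-ablation CT are withheld until this form is locked.
- **Step 2, prediction revealed:** observed minus predicted is reported from the locked values. The recorded effects are then classified as inside or outside the predicted zone, which serves secondary endpoint 2.

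Locating effects relative to the electrode in step 1 is what allows the predicted boundary to be applied in step 2 without a fresh, unmasked reading.

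The cost is a few sentences in 7.2.6, a two-part pathology form and a slightly later comparison. It needs no additional reader and no added procedure for subjects.

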#### 7.2.7 Post-surgical blood draw

A post-surgical blood draw will be taken 2-4 weeks post-surgery to assess for immune response indicators.

---

 M.A.J. Gorris, et al. Eight-Color Multiplex Immunohistochemistry for Simultaneous Detection of Multiple Immune Checkpoint Molecules within the Tumor Microenvironment *J Immunol* January 1, 2018, 200 (1) 347-354

## 8 RISK/BENEFIT ANALYSIS

Spiration has conducted an analysis of the potential benefits and risks of the ANET procedure and device operation on the patient population as defined in section 6 of this protocol.

### 8.1 Justification for Investigation

The safety of subjects participating in first in man studies is the paramount consideration in proceeding to clinical trials in man. Such subjects would not normally be expected to derive any therapeutic benefit.

The lack of observed safety effects from the pre-clinical studies have provided the benchmark for safety in this first in human study. The study has been designed to optimize knowledge gained regarding ablation therapy in human cancerous tissue without involving excessive numbers of subjects and while ensuring the safety of patients.

The study design is a treat/resect design wherein the ablated tissue is fully within the part of the lung being surgically removed and represents the standard of care for these patients with primary lung cancer.

Lastly, the study has limited the number of trial sites being used to incorporate centers of excellence in the treatment of lung cancer. All of these sites will be further trained on the use of the ANET device to minimize safety events.

### 8.2 Benefits

There are no direct benefits to patients in this study. However, information from this study may help patients in the future with Stage I, II lung cancer and with pulmonary metastasis who are not suitable for surgical intervention.

### 8.3 Risks

- Risks of ANET ablation procedure and device are listed in Table 2, section 9.2 of this protocol.
- Patients will receive up to 3 additional CT's as a result of this study. These include a CT prior to and after ANET ablation. An additional CT may be taken to confirm needle location during the ANET ablation procedure.

#### 8.3.1 Risk Management

Risks associated with the use of the ANET device are minimized through device design, Investigator selection and training, pre-specified subject eligibility requirements and study monitoring to ensure adherence to this investigational plan. Specific strategies include:

- Clearly defining the subject inclusion/exclusion criteria

- Prior to treatment, adequate cancer specimen sufficient for mutational analysis will be collected
- AEs will be reported per section 9 of this investigational plan and will be reported and monitored throughout the course of the study
- The sites will be notified if unexpected adverse device effects and other safety concerns that could negatively impact the safety of subjects if such issues arise
- Ensuring that treatment and follow-up of subjects is consistent with standard and current medical practice.

## 9 ADVERSE EVENTS

### 9.1 DEFINITIONS (from ISO/FDIS 14155)

#### 9.1.1 Adverse Event (AE)

Any untoward medical occurrence, unintended disease or injury, or untoward clinical signs (including abnormal laboratory findings) in subjects, users or other persons, whether or not related to the investigational medical device which includes:

- a. events related to the investigational medical device or the comparator; and
- b. events related to the procedures involved

For users or other persons, this definition is restricted to events related to investigational medical devices.

#### 9.1.2 Adverse Device Effect (ADE)

Adverse event related to the use of an investigational medical device.

NOTE 1- This includes any adverse event resulting from insufficiencies or inadequacies in the instructions for use, the deployment, the implantation, the installation, the operation, or any malfunction of the investigational medical device.

NOTE 2- This includes any event that is a result of a use error or intentional misuse.

#### 9.1.3 Device deficiency

Inadequacy of a medical device related to its identity, quality, durability, reliability, safety or performance, such as malfunction, misuse or use error and inadequate labeling.

#### 9.1.4 Investigational medical device

Medical device being assessed for safety or performance in a clinical investigation

NOTE: This includes medical devices already on the market that are being evaluated for new intended uses, new populations, new materials or design changes.

#### 9.1.5 Serious Adverse Device Effect (SADE)

Adverse device effect that has resulted in any of the consequences characteristic of a serious adverse event.

#### 9.1.6 Serious Adverse Event (SAE) (see Table 3.0 of Protocol Defined Serious

Adverse Events, below)

Adverse event that:

- a) led to a death,
- b) led to a serious deterioration in health that either:
  - 1) resulted in a life-threatening illness or injury, or
  - 2) resulted in a permanent impairment of a body structure or a body function, or
  - 3) required in-patient hospitalization or prolongation of existing hospitalization, or
  - 4) resulted in medical or surgical intervention to prevent life threatening illness or injury or permanent impairment to a body structure or a body function.
- c) led to fetal distress, fetal death or a congenital abnormality or birth defect.

NOTE 1: This includes device deficiencies that might have led to a serious adverse event if a) suitable action had not been taken or b) intervention had not been made or c) if circumstances had been less fortunate. These are handled under the SAE reporting system.

NOTE 2: A planned hospitalization for pre-existing condition, or a procedure required by the Clinical Investigation Plan, without a serious deterioration in health, is not considered to be a serious adverse event.

#### 9.1.7 Unanticipated Serious Adverse Device Effect (USADE)

Serious adverse device effect which by its nature, incidence, severity or outcome has not been identified in the current version of the risk analysis report.

NOTE: Anticipated: an effect which by its nature, incidence, severity or outcome has been previously identified in the risk analysis report. Adverse events listed in Table 2 below are considered anticipated for this study.

#### 9.2 Protocol Defined Potential Adverse Events

The following list of adverse events are anticipated given the nature of the EBUS procedure and the investigational device. Potential adverse event terms in Table 2 are referenced from MedDRA release Version 23.0. All terms are Preferred Terms (PT).

**Table 2: Potential Adverse Events**

MedDRA term
Ablation site reactions

MedDRA term
(MedDRA term: Administration site reactions)
Abscess formation (MedDRA term: Wound Abscess)
Anaesthetic complication
Arrhythmia
Atelectasis
Bronchial obstruction
Bronchopulmonary hemorrhage
Bronchospasm
Burning or charring – unintended (MedDRA term: Burn local)
Cardiac arrest
Death
Device failure
Dyspnea
Electric shock
Esophageal hemorrhage
Hematoma (MedDRA term: Post-procedural hematoma)
Haemolysis
Haemoptysis
Hemorrhage
Hemothorax
Hypoxemia
Infection (acute)
Laryngeal spasm
Localized allergic reaction or irritant reaction (MedDRA term: Administration site hypersensitivity)
Microbubble/air embolism
Pleural effusion
Pleuritic pain
Pneumo-mediastinum
Pneumonia
Pneumonitis
Pneumothorax
Post-procedural hemorrhage
Postoperative thoracic procedure complication

MedDRA term
Pulmonary edema
Pulmonary embolism
Pulmonary fistula
Respiratory failure
Systemic toxicity
Soft tissue necrosis
Tumor recurrence (MedDRA term: Neoplasm recurrence)
Tumor seeding (MedDRA term: Treatment related secondary malignancy)

**Table 3: Adverse Event Categories**

ADVERSE EVENTS	Non-device-related	Device- or procedure-related	
Non-serious	Adverse Event (AE)a (3.2)	Adverse Device Effect (ADE) (3.1)	
Serious	Serious Adverse Event (SAE)b (3.37)	Serious Adverse Device Effect (SADE) (3.36)	
		Anticipated	Unanticipated
		Anticipated Serious Adverse Device Effect (ASADE) (3.42, Note)	Unanticipated Serious Adverse Device Effect (USADE) (3.42)

a Includes all categories.
 
b Includes all categories that are serious.
			

### 9.1 Adverse Event (AE) Reporting by Investigator

Peri-procedural adverse events, defined as from the start of the EBUS bronchoscopy through the planned surgical resection, will be collected up to 30 days post procedure using the AE paper case report form. AEs shall be reported in accordance with study institution requirements, local vigilance systems, 21CFR 803 21CFR 812.46, 21CFR 812.140, and 21CFR 812.150, and ISO 14155:2011, sections 8.2.5 and 9.8.

Since this is a limited pilot study, there is no Data Safety Monitoring Board. In the event of an incidence of massive hemoptysis, acute respiratory distress, or a death that is device or ANET procedure related, as defined by the Principal Investigator, the study will be paused and the IRB and FDA will be notified.

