### 5.2 General Description of Study

[figure not shown]
After consent and evaluation of all inclusion and exclusion criteria, subjects will be enrolled in the study. The subject will undergo standard pre-operative testing, per the study institutional requirements. At that time, subject vital signs will be recorded. The subject will be prepped for bronchoscopy.

A pre-ablation chest CT will be taken. The target nodule/tumor will be accessed via EBUS bronchoscopy, which may be guided and confirmed with Cone Beam CT, Intra-operative CT, or fluoroscopy, and ablated using the ANET Electrosurgical Applicator. Following ablation, there will be a bronchoscopic exam of the treated region and repeat chest CT will be taken.

Immediately following bronchoscopy and ablation of the target tissue, the subject will undergo the planned surgical resection. The ablated tumor will be prepared for histopathological and immuno-histochemistry evaluation to assess the area of ablated tissue. Subjects will be followed peri-operatively. There is no long-term follow-up since the ablated tissue will be resected during the surgical procedure, however adverse events will be captured through 30 days post procedure.

Blood will be drawn pre and post-ablation and 2-4 weeks post-surgery, per the ANET Blood Draw Lab Manual, DN0042775, to evaluate for potential immune response indicators. Blood specimens will be analyzed by a core laboratory to characterize cells important in immune responses and the disease process.

A study diagram is shown in Figure 4 below.

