#### 7.2.1 Pre-ablation CT and blood draw

A pre-ablation chest CT will be taken prior to ANET ablation, may be performed while the subject is under general anesthesia.

A pre-ablation blood draw will be taken to assess for immune response indicators

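### Adverse event collection opens at the EBUS bronchoscopy, after the study-added CT in the described order, so non-serious events from that step have no stated route onto the AE form

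*Combined protocol and SAP*

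**What the plan says.** The protocol has two sections numbered 9.1. The one headed Adverse Event (AE) Reporting by Investigator sets the collection window. It describes peri-procedural events as "defined as from the start of the EBUS bronchoscopy through the planned surgical resection", with collection continuing to 30 days after the procedure. This point concerns only where that window opens.

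Section 5.2 gives the order of the day: "A pre-ablation chest CT will be taken. The target nodule/tumor will be accessed via EBUS bronchoscopy". Section 7.2.1 adds: "A pre-ablation chest CT will be taken prior to ANET ablation, may be performed while the subject is under general anesthesia". Section 8.3 lists the scan among the study's risks: "Patients will receive up to 3 additional CT's as a result of this study. These include a CT prior to and after ANET ablation".

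The AE definition in section 9.1.1 covers "events related to the procedures involved" and sets no start time. Table 2 lists "Anaesthetic complication" among the anticipated events. Section 12 says the sample of 10 is meant to yield both procedural and device-related AE information, summarized without a hypothesis.

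**The concern.** The collection window is narrower than the definition it serves. If the subject has the study CT, perhaps under general anesthesia, and the window opens only when the bronchoscopy starts, a minor event in between is an AE by definition but falls outside the collection rule. The trial's main product is a list of adverse events in at most 10 subjects, so a gap in what is listed bears directly on that product.

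There is a second, weaker consequence for attribution. Several Table 2 terms, such as arrhythmia, hypoxemia and bronchospasm, could begin before a bronchoscope is introduced. If such a problem persists into the bronchoscopy, and nothing on the AE form shows that it was already there, it may be read as arising from the device or the procedure.

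**Working it through.** **No planned figure to reproduce.** Section 12 calls the sample size arbitrary and gives no error rate, power or effect size. The check is a comparison of sections, followed by a short illustration of scale.

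**Step 1: is there a study procedure before the window?** Section 5.2 describes the CT and then EBUS access, and section 7.2.1 precedes the ANET procedure in 7.2.2. Section 8.3 shows that the CT is done because of the study. On that order, the CT and any anesthesia given for it fall before the window. Two limits apply:
- Section 7.2.1 strictly requires the CT to precede ablation, not EBUS, so its place before EBUS rests on narrative order.
- The pre-ablation blood draw is also tied only to ablation, so its timing relative to EBUS is not fixed.

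**Step 2: do other sections close the gap?**

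| Section | Start point | Covers a non-serious event before EBUS? |
|---|---|---|
| 9.1 AE Reporting by Investigator | Start of EBUS bronchoscopy | No |
| 9.2 SAE Reporting by Investigator | None stated | No, serious events only |
| 8.3.1 Risk Management | Whole study, but as section 9 provides | Unclear, since it leads back to 9.1 |
| 9.1.1 AE definition | None stated | Yes by definition, but it is not a collection rule |

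These sections do not agree on when capture begins. Non-serious events before EBUS have no stated route onto the form.

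**Step 3: could an earlier problem reach the device-related count?** The Event Causality text classes an event as related when its timing fits the device or the procedure, taken together. Table 3 also pools device- and procedure-related events under the adverse device effect headings. Section 5.2 provides standard pre-operative testing and vital signs, and the CT is a baseline image. Beyond these, no record of symptoms or conditions present just before EBUS is specified. Misclassification is possible, but nothing in the documents makes it certain.

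**Step 4: scale.** Exact (Clopper-Pearson) 95% intervals for n = 10:
- 0/10 = 0%, interval 0% to 30.8% (upper limit 1 − 0.025^(1/10) = 0.3085).
- 1/10 = 10%, interval 0.3% to 44.5%.

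One reclassified subject therefore moves the estimate by 1/10 = 10 percentage points.

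The documents give no rate for events before EBUS. Under an assumed per-subject rate p, the chance of at least one such event in 10 subjects is 1 − (1 − p)^10:

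| Assumed p | Chance of at least one in 10 |
|---|---|
| 1% | 9.6% |
| 2% | 18.3% |
| 5% | 40.1% |
| 10% | 65.1% |

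These are chances that an event occurs, not that it is misclassified. The second chance cannot exceed the first.

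**The case against.** The primary endpoint is device-related events around the procedure, and what happens before EBUS happens before the device is used. On that view the window fits its endpoint and an earlier start is a preference. This stands as far as it goes: no device event is missed. It does not answer section 12, which also asks for procedural events, or section 9.1.1, which defines them as AEs.

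A reader might infer that harms of the study CT go wholly unrecorded, or that nothing is known of the subject's state before the device is introduced. The documents support neither. SAE reporting has no start limit, and pre-operative testing, vital signs and the CT give some baseline.

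A reader might also take it as settled that the blood draw precedes EBUS, or that anesthesia is induced for the CT. The first is not stated. The second is only permitted, and the planned resection follows immediately after bronchoscopy in any case.

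On attribution, no section tells the investigator to re-date an earlier event to the bronchoscopy. Section 9.1.2 requires a device effect to be related to use of the device, and the guidance on multiple events directs sequelae to their primary cause. These points reduce the risk. What remains comes mainly from the timing-only causality scale, which does not separate device from procedure. The late start adds to it by leaving no event-level record of what was already present.

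Finally, a shift of 10 percentage points per subject holds for any event in a sample of 10. It shows sensitivity and is not evidence that the problem will occur.

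**Conclusion.** The point holds in a limited form. As written, the window omits non-serious events from a study-added step that the protocol's own definition covers, and the sections on AE collection, SAE reporting and risk management state no common start point. This rests on the CT preceding EBUS as section 5.2 describes. If a site performed the CT after the bronchoscopy began, the CT step would fall inside the window.

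The effect on the primary endpoint is indirect: a possible misattribution, at most one subject in 10 for each such event, with a frequency that the documents do not allow anyone to estimate. It would be wrong to conclude that the device-related count is biased. It would also be wrong to conclude that events starting before applicator insertion should be barred from that count. Section 9.1.2 includes effects of inadequate instructions, installation and use error, so an onset cut-off could remove genuine device effects. The change is worth making because AE information is the study's main output and the correction is small.

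**What to change.** In the section on AE reporting by the investigator, start AE capture at the first study-specific procedure: the pre-ablation blood draw, the pre-ablation CT, or anesthesia given for that CT, whichever comes first. Align section 8.3.1 and the section on SAE reporting to the same start point.

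Record conditions present before EBUS as baseline. On the AE form, record onset in one of three phases:
- before bronchoscopy;
- from bronchoscopy start to applicator insertion;
- from applicator insertion onward.

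In section 12, state that device-related events will be listed with their onset phase shown. Do not exclude events automatically by phase. Relatedness should stay with the causality assessment and the device-effect definition in section 9.1.2.

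The cost is some aligned wording, a short baseline entry, one added field on the AE form, and probably a few more procedure-related events in the listing. Sample size and visit schedule do not change.
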